#### 8.6 Trial Outcome Measures

#### 8.6.1 Primary outcome measure

**MAST-PROPHYLAXIS:** Occurrence of an acute symptomatic seizure within 2 weeks post-TBI. **MAST-DURATION:** Occurrence of late PTS within 24 months post-TBI

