#### 8.6.2 Secondary outcome measures (both trials)

- Occurrence and time to PTS within 24 months post-TBI (MAST-PROPHYLAXIS ONLY)
- Extended Glasgow Outcome Scale, Neurobehavioral Symptom Inventory, quality of life (EQ-5D-5L), and Liverpool Adverse Events Profile at 6, 12, 18 and 24 months.
- Economic evaluation
- Frequency of PTS
- Mortality at 6, 12, 18 and 24 months.
- Adverse events of special interest during treatment.

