## MAST-DURATION

Patients who fulfil the eligibility criteria will be randomly assigned to a maximum of 3 months OR a minumum of 6 months duration of a clinically prescribed AED (phenytoin or levetiracetam, choice of drug at clinician's/site's local option). The distribution between trial populations will be 1:1 (<3 months:>6months). In the event of a seizure occurring within the trial period, treatment will continue as per local clinical guidelines regardless of the treatment arm. If treatment management changes within the trial period, patients will remain in the trial.

A secure electronic system will be used for the randomisation of suitable patients. Suitably trained staff will access the secure site and enter the patient details. 24-hour telephone support will be provided for randomisation and eligibility criteria by Trial Investigators or suitable trained delegated persons. Allocation will be stratified by depressed skull fracture (yes / no), intradural lesion (yes / no) and initial severity of injury (GCS 3-8, GCS 9-15).

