#### 14.1 Response criteria

#### 14.1.1 Mortality

This will be measured from the date of randomisation to the 24 month follow up and will be reported for all deaths due to all causes. The cause of death is to be recorded if known.

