## 16 Statistics

### 16.1 Statistical methods

The main statistical analysis will be performed on an intention-to-treat basis, which will include all randomly assigned participants.

The primary endpoint (occurrence of PTS) is binary (yes / no). The primary analysis will estimate the absolute difference between the active treatment groups and control in terms of the incidence of PTS using logistic regression with an additive link, adjusting for baseline covariates (subdural haematoma (yes / no), number of lobes with a contusion (none / one / two / more than two), craniotomy or craniectomy (yes / no), depressed skull fracture (yes / no), initial severity of injury GCS 3-8 / 9-15, intradural lesion (yes / no) and will furnish the estimates with 95% confidence intervals. MAST DURATION will use a standard 2-sided p-value compared to a 5% significance level; MAST-PROPHYLAXIS will adjust for multiple testing using Dunnett's test at an overall 5% significance level stipulating that the smaller of the 2-sided p-values must be less than 2.7% to achieve statistical significance. A direct comparison between active arms (phenytoin vs levetiracetam) in MAST-PROPHYLAXIS will be a secondary analysis. The baseline covariates will be those used to stratify the randomisation: depressed skull fracture (yes / no), intradural lesion (yes / no) and initial severity of injury (GCS 3-8, GCS 9-15). Site will be handled as a random effect as there are anticipated to be 29 sites.

Sensitivity analyses will be performed to assess the influence of missing data and deviations from the intention-to-treat principle.

The GOSE will be analysed with an ordinal method adjusting for baseline covariates. Further secondary endpoints will be summarized using appropriate techniques according to whether the variable is binary, categorical, continuous or time-to-event. Categorical and binary variables will be summarized using bar charts, frequency tables and comparisons made using logistic regression.

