Continuous variables will be summarized, broken down by treatment arm, using Box plots, mean, median, SD, max, min and compared using linear regression. Time-to-event variables will be summarized using Kaplan-Meier plots, and compared using the log-rank test. Predefined subgroups for exploratory analyses will be: subdural haematoma (yes / no), number of lobes with a contusion (none / one / two / more than two), craniotomy or craniectomy (yes / no), depressed skull fracture (yes / no), initial severity of injury GCS 3-8 / 9-15, intradural lesion16.1 (yes / no), lesion site (temporal, insular, frontal, parietal, occipital, basal ganglia, thalamo-capsular, posterior fossa) and lesion type (extradural hematoma, acute subdural haematoma, contusion, chronic subdural haematoma, diffuse axonal injury, skull vault fracture, other). A detailed statistical analysis plan will be prepared by the study statistician without reference to the unblinded data.

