#### 16.5 **Procedure to account for missing or spurious data**

For the primary analysis missing data will be assumed to be missing at random. A sensitivity analysis will be carried out by performing a complete case analysis. As the relevant covariates need to be recorded before the patient can be randomised, we aim to have minimal missing baseline data. There is also an excellent track record for UK-led neurosurgical studies in achieving extremely high rates for follow-up (STICH, STICH II and RESCUEicp studies).

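### In MAST-PROPHYLAXIS, summarising time to seizure by Kaplan-Meier overstates the absolute 24-month risk if deaths are censored, because death before a seizure is a competing event

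*Protocol*

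**What the plan says.** Section 16.1 sets the method for time-to-event outcomes among the further secondary endpoints: "Time-to-event variables will be summarized using Kaplan-Meier plots, and compared using the log-rank test". No stratification, covariate adjustment or competing-risk method is stated for them. Section 8.6.2 supplies the seizure outcome of that type, and limits it to one trial: "Occurrence and time to PTS within 24 months post-TBI (MAST-PROPHYLAXIS ONLY".

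The primary endpoints are handled differently. Section 16.1 says "The primary endpoint (occurrence of PTS) is binary (yes / no") and analyses it by regression with an additive link, adjusted for baseline covariates. That covers the 2-week seizure endpoint in MAST-PROPHYLAXIS and, in MAST-DURATION, "Occurrence of late PTS within 24 months post-TBI" (section 8.6.1).

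Death is expected. All-cause mortality is an outcome at 6, 12, 18 and 24 months (sections 8.6.2 and 14.1.1), and a GCS of 3-8 is one level of a randomisation stratum (section 9.3). Section 9.2 excludes unsurvivable injury, which reduces deaths but does not remove them.

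On missing data, section 16.5 says "For the primary analysis missing data will be assumed to be missing at random" and then "A sensitivity analysis will be carried out by performing a complete case analysis". No section says whether a participant who dies without a seizure is censored, missing, counted as having no PTS, or treated as having had a competing event.

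**The concern.** Read as an estimate of risk, one minus Kaplan-Meier with deaths censored answers a hypothetical question: how many would have a seizure if nobody could die first. The proportion of randomised patients who actually have a seizure by 24 months is the cumulative incidence, and the Kaplan-Meier figure is never below it. The two differ whenever some seizures occur after some seizure-free deaths.

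This matters because the trial states its effects as absolute differences in seizure incidence, which is the scale that is distorted. The 24-month figure read from the curve would not match the binary 24-month occurrence reported for the same outcome. If mortality differed between arms, the gap would also differ between arms.

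A second, smaller point is that the stated time-to-event comparison makes no use of the factors by which the trial randomises, although the primary analysis does.

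**Working it through.** **The plan's own figures.** The plan gives no figure for this endpoint. Its power statements concern the binary primaries, and they reproduce:
- MAST-DURATION, 188 per arm, 25% versus 12%, two-sided 5%: power 0.904 (stated 90%).
- MAST-PROPHYLAXIS, 358 per arm, 11% versus 4%, two-sided 2.7%: power 0.912 (stated 91% for a single comparison).

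The Kaplan-Meier sentence does not enter either calculation.

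**Inputs for the size of the effect.**
- F is the true cumulative incidence of seizure by 24 months. None is given for MAST-PROPHYLAXIS, so 11% and 12% are illustrations. In section 16.3, 11% is that trial's assumed control rate for the 2-week endpoint, and 12% is the assumed 24-month rate in the longer-course arm of MAST-DURATION.
- D is the proportion dying by 24 months without a prior seizure. It is not given, so 5% to 30% is assumed.

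**Formulas.** The proportion alive and seizure-free at 24 months is 1 - F - D. If the two cause-specific hazards are proportional over time, seizures account for a share F/(F + D) of the total cumulative hazard. Hence

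Kaplan-Meier risk = 1 - (1 - F - D)^(F/(F + D)).

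If every seizure-free death preceded every seizure, the Kaplan-Meier risk would be F/(1 - D), the upper bound. If every such death followed the last seizure, it would equal F and there would be no overstatement.

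**Example.** For F = 0.11 and D = 0.05, the exponent is 0.11/0.16 = 0.6875, and 1 - 0.84^0.6875 = 0.1130, an excess of 0.30 points.

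| Assumed D | F = 11%: Kaplan-Meier (excess, points) | Upper bound | F = 12%: Kaplan-Meier (excess, points) | Upper bound |
|---|---|---|---|---|
| 5% | 11.30% (0.30) | 11.58% | 12.32% (0.32) | 12.63% |
| 10% | 11.62% (0.62) | 12.22% | 12.67% (0.67) | 13.33% |
| 15% | 11.96% (0.96) | 12.94% | 13.05% (1.05) | 14.12% |
| 20% | 12.34% (1.34) | 13.75% | 13.47% (1.47) | 15.00% |
| 30% | 13.20% (2.20) | 15.71% | 14.41% (2.41) | 17.14% |

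In relative terms the overstatement is about 3% of the true risk at D = 5% and about 20% at D = 30%.

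**Binary endpoints, conditional only.** If participants who die seizure-free were classed as missing and left out, the observed proportion with a seizure would be F/(1 - D). Taking MAST-DURATION's planning rates as true, with D = 10% in both arms, 25% would read 0.25/0.90 = 27.8%, 12% would read 0.12/0.90 = 13.3%, and the 13-point difference would read 0.13/0.90 = 14.4 points. If those participants are counted as having no PTS, there is no inflation.

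**The case against.** The case on the other side has four parts.

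- **Scope.** The sentence is a general line about time-to-event variables, and the only seizure outcome it reaches is one secondary endpoint in one trial. A reader might infer that the 24-month risk in MAST-DURATION, or the 2-week risk in MAST-PROPHYLAXIS, will be overstated too. The document does not support that, because both primaries are binary and are analysed by regression. This objection stands.
- **The test.** A reader might infer that the log-rank test is invalid. It is not. With deaths censored it tests equality of cause-specific hazards, provided other censoring is non-informative, and the cause-specific Cox model recommended below censors deaths in the same way. The bias lies in the height of the curve. An unadjusted test is also valid, and the absence of adjustment is inferred only from silence. Using the randomisation factors is therefore an improvement and corrects no error.
- **Missing data.** A reader might infer that section 16.5 treats deaths as missing at random. It does not say so. Counting a seizure-free death as no PTS fits the present text, and coding rules of this kind are commonly left to the SAP, which section 16.1 promises. This limb survives only as a clarification. It is worth making because the complete-case sensitivity analysis would drop the same participants if they were classed as missing, and so could not reveal the problem.
- **Size.** A reader might start from 25% and reach a larger figure (0.7 to 5.4 points under the same formula). But 25% is the MAST-DURATION control rate, for an endpoint to which Kaplan-Meier is not applied.

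The objection does not remove the central point. Kaplan-Meier is a stated choice, the trial expects deaths, and the choice is a poor one for describing absolute risk of a non-fatal event.

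**Conclusion.** The point holds for time to PTS within 24 months in MAST-PROPHYLAXIS: a Kaplan-Meier summary that censors deaths will overstate the absolute seizure risk. At an illustrative true incidence of 11% to 12%, the excess is about 0.3 to 2.4 points for assumed seizure-free mortality of 5% to 30% under proportional hazards. It is under 1 point while that mortality is 10% or less.

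The size rests on three things the document does not give: mortality, the 24-month seizure rate in this trial, and the timing of deaths relative to seizures. If most seizures come before most deaths, the excess shrinks towards zero. If deaths come first, it moves towards the upper bounds in the table.

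The between-arm log-rank test, the sample sizes and the two binary primary analyses are not affected by the Kaplan-Meier sentence. The binary risks would be inflated only if seizure-free deaths were treated as missing, which the protocol does not say.

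**What to change.** - In section 16.1, replace the Kaplan-Meier summary of time to PTS with Aalen-Johansen cumulative incidence by arm, treating death without a prior seizure as a competing event.
- Compare arms by cause-specific Cox regression adjusted for depressed skull fracture, intradural lesion and GCS group, or by a log-rank test stratified on those factors.
- In section 16.5, limit the missing-at-random assumption to outcomes missing for reasons other than death. State that participants who die seizure-free count as having no PTS in the binary endpoints.
- Add a seizure-or-death composite as a sensitivity analysis, so that counting such deaths as no PTS does not hide a difference in mortality.

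The cost is a few sentences, slightly more analysis work and one extra sensitivity table. Mortality is already an outcome, the methods are in standard software, and the sample size does not change. The change is best made before unblinded data are seen.

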#### 16.2 Interim analyses

The primary purpose of the pilot is to assess recruitment rates rather than to make sample size adjustments, see section 8.3 for further details.

An interim analysis (blinded to all except the IDMC: Independent Data Monitoring Committee) may be performed after an appropriate number of patients have observed 14 days follow up for Prophylaxis and 24-month follow-up for DURATION, shortly before recruitment is scheduled to be halted, in order to confirm the sample size. The TSC, IDMC and statistical team will agree jointly on the most appropriate timing of this interim analysis, taking into account the case mix and parameters the IDMC wishes to estimate. If the sample size needs to be revised, we are able to incorporate the uncertainly in absolute seizurerates of 11% for MAST-PROPHYLAXIS and 25% for MAST-DURATIONin order to achieve an acceptable conditional power as

determined by the IDMC.

The interim analysis will be outlined in the IDMC Charter.

#### 16.3 Number of Participants to be enrolled

A 12% drop-out rate is assumed in both trials.

### MAST-PROPHYLAXIS

According to the available evidence (5,6), a treatment effect of 7% can be expected with seizure prophylaxis. We will attempt to reproduce these findings in a multi-centre setting across the NHS. Recruiting 1221 patients overall will provide 358 observations per arm. Assuming seizure rates of 4% in both active arms and 11% in control will provide 90% power to achieve significance in both comparisons. Alternatively, if only one active arm has a seizure rate of 4% and the other the same rate as control, then there will be 91% power to achieve significance in that individual comparison. The expected average annual recruitment is 15-20 patients / site. We will aim to roll out the trial in 29 adult trauma-receiving hospitals in the UK. According to the timeline presented below, the recruitment will be completed in 3 years.

#### MAST DURATION

A course of phenytoin or levetiracetam (up to 3 months) for patients with PTS in the acute phase. Hence, we are starting from the premise that the shorter AED duration is 'standard' practice. The longer AED duration course will potentially decrease the PTS rate. Therefore, the proposed study will be a superiority trial. In view of the potential for increase in side effects with a longer course, we will aim for a relatively large treatment effect of 13% (NNT 7.7), as this is felt necessary in order to lead to a change in clinical practice in the 'real -world'.

Recruiting 428 patients overall will provide 188 observations per arm. Assuming seizure rates of 12% and 25% in the intervention and control arm will provide 90% power. The expected average annual recruitment is 5-10 patients / site. We will aim to roll out the trial in 29 adult trauma-receiving hospitals in the UK. According to the timeline presented below, the recruitment will be completed in 3 years.

#### 16.4 Criteria for the premature termination of the trial

There are no defined criteria for the premature discontinuation of the trial. However the DMC and TSC will make recommendations on the discontinuation of the trial following review of the ongoing data presented at regular scheduled meetings.

#### 16.5 **Procedure to account for missing or spurious data**

For the primary analysis missing data will be assumed to be missing at random. A sensitivity analysis will be carried out by performing a complete case analysis. As the relevant covariates need to be recorded before the patient can be randomised, we aim to have minimal missing baseline data. There is also an excellent track record for UK-led neurosurgical studies in achieving extremely high rates for follow-up (STICH, STICH II and RESCUEicp studies).

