# Stop:

Less than 30% recruitment achieved. The decision to progress will be made by the Trial Steering Committee in association with the HTA secretariat.

If the loss to follow-up (for those who have observed 6 months follow-up) exceeds 20%, without an identifiable and correctable reason it would not be feasible to progress to the substantive phase without substantial changes to the study design.

If either the DURATION or PROPHYLAXIS trial fails to recruit to target and subsequently doesn't proceed to stage 2, then recruitment to the other trial will continue under this protocol as appropriate.

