# 11.7 Long-Term Follow-up Assessments

Participants will be followed up for 24 months post randomisation by postal questionnaire. However, if after approximately 2 weeks the questionnaire has not been returned then patients will be followed up by telephone. If the time point after an assessment exceeds 8 weeks, and there is no response, then the patient will be deemed as lost to that follow up. Where patients attend for a routine clinical follow-up they will be reviewed.

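### The one missing-data sensitivity analysis that section 16.5 names, complete case, needs the same or a stricter assumption than the missing-at-random primary analysis, so it cannot test outcome-related loss; this matters mainly for MAST-DURATION

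*Protocol*

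**What the plan says.** Protocol section 16.5 sets the assumption, "For the primary analysis missing data will be assumed to be missing at random", and follows it directly with the check, "A sensitivity analysis will be carried out by performing a complete case analysis". It adds that covariates have to be recorded before randomisation, so little baseline data should be missing, and it cites good follow-up in earlier UK neurosurgical studies.

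Section 16.1 sets the population, "The main statistical analysis will be performed on an intention-to-treat basis, which will include all randomly assigned participants", and makes a general promise without naming a method: "Sensitivity analyses will be performed to assess the influence of missing data and deviations from the intention-to-treat principle".

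On the amount of loss, section 16.3 states "A 12% drop-out rate is assumed in both trials". The pilot rules in section 8.3 raise feasibility only "If the loss to follow-up (for those who have observed 6 months follow-up) exceeds 20%, without an identifiable and correctable reason". Section 11.7 says how loss arises after discharge: "If the time point after an assessment exceeds 8 weeks, and there is no response, then the patient will be deemed as lost to that" follow-up.

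The economic section (16.6) swaps complete case and multiple imputation as base case and sensitivity analysis. No section names an analysis that departs from MAR.

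**The concern.** A sensitivity analysis is useful when it relaxes the assumption on which the main analysis depends. Here the untestable assumption is that patients lost to follow-up have the same seizure risk as observed patients with the same arm and covariates. Complete case does not relax this. If loss depends on the outcome, both analyses are biased, and their agreement could be read as reassurance.

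Informative loss is plausible in MAST-DURATION. Patients know their allocation. The outcome is collected over 24 months and depends largely on patients responding after discharge. The protocol itself says that late seizures affect quality of life, work and driving (6.1), and it anticipates more side effects with the longer course (16.3). Either could affect response, and not equally in the two arms. At stake is whether a positive but moderate MAST-DURATION result could be reported as robust to missing data when that was never tested.

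**Working it through.** **1. The plan's own figures.** Section 16.3 says "Recruiting 428 patients overall will provide 188 observations per arm". Check: 428 × 0.88 / 2 = 188.3. A pooled two-sided test at 5% with 188 per arm and rates of 12% and 25% has 90.4% power (stated: 90%). For MAST-PROPHYLAXIS, 1221 × 0.88 / 3 = 358.2 per arm. Both reproduce. Lost per arm: 428/2 − 188 = 26 in MAST-DURATION and 1221/3 − 358 = 49 in MAST-PROPHYLAXIS.

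**2. Why complete case does not test the assumption.** Let R = 1 if the outcome Y is observed. Complete case needs P(R = 1 | Y, arm, covariates) not to depend on Y. A MAR analysis with the same variables needs exactly that. A MAR analysis that also uses interim data needs it only after conditioning on those data as well. So the assumption behind complete case is the same or stricter, never weaker in the direction of informative loss.

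**3. Size of a hidden bias (loss rates assumed).** True rates are 12% v 25%. Long-course patients with seizures are lost at 30% and everyone else at 10%.
- Observed long-course rate: 0.12 × 0.70 / (0.12 × 0.70 + 0.88 × 0.90) = 0.084 / 0.876 = 9.6%.
- Complete-case difference: 25.0 − 9.6 = 15.4 points, against a true 13.0, a bias of about 2.4 points.
- In 400 simulated trials, complete case and MAR imputation on arm and covariates both gave 15.3 points, with correlation 0.997.
- A separate simulation had no true effect and stronger informative loss in one arm (40% of those with seizures lost v 4% of those without). Complete case gave a spurious 7.8 points and MAR imputation 7.3.

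**4. Tipping counts, MAST-DURATION.** Each arm has 214 patients, and lost control patients have seizures at 25%, so control has 47 + 6.5 = 53.5 events. Let k be the number of seizures among the 26 lost long-course patients. The test is Z = (p_C − p_L) / √[p̄(1 − p̄)(2/214)], where p̄ is the pooled rate.

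| Observed rates | Observed long-course events | k | p_L | Z | p |
|---|---|---|---|---|---|
| 25% v 12% (design) | 22.56 | 14 | 17.1% | 2.01 | 0.045 |
| 25% v 12% (design) | 22.56 | 15 | 17.5% | 1.88 | 0.060 |
| 25% v 16% (assumed) | 30.08 | 6 | 16.9% | 2.07 | 0.039 |
| 25% v 16% (assumed) | 30.08 | 7 | 17.3% | 1.94 | 0.052 |

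With events rounded to whole patients the design-effect count is 14 rather than 15. Expected seizures under MAR are 26 × 0.12 = 3.1 and 26 × 0.16 = 4.2. In the 16% case, complete case on 188 per arm gives p = 0.031.

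**5. The same question as odds ratios.** Multiply the seizure odds of lost long-course patients by 2, 3 or 5, with lost control patients as observed. At the design effect the difference is 11.9, 10.9 or 9.5 points (p = 0.002, 0.004, 0.014). At 25% v 16%, an odds ratio of 2 already gives 7.6 points (p = 0.055).

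**6. MAST-PROPHYLAXIS.** With 407 per arm, 49 of them lost, and 11% v 4%, significance is lost at 13 of 49 when p is held to 2.7%, or 15 of 49 at 5% (about 2 expected). With an assumed active-arm rate of 5.9%, the counts are 6 and 8 (about 3 expected). At the design rates an odds ratio of 5 leaves 5.4 points (p = 0.005).

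**The case against.** The strongest reply has five parts.

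- **Complete case is not said to be the only check.** This is right. Section 16.5 names one analysis without excluding others, and section 16.1 promises sensitivity analyses in general terms. A reader might infer that the protocol rules out any other check, or that the two sections contradict each other. The text supports neither, and an analysis plan not shown here may add more. What stands is that 16.5 chose a method, and that method cannot answer the question of informative loss.
- **The two analyses need not be nearly identical.** Also right. MAST-DURATION has follow-up at 6, 12, 18 and 24 months, and loss is defined per time point. A MAR model using interim data can differ from complete case. Under one assumed pattern, with loss depending on an already recorded seizure, MAR recovered the true 13.0 points while complete case gave 15.3. Such a gap reflects reliance on interim data and is still no test of loss that depends on the unseen outcome.
- **Seizures are not ascertained by post alone.** Sections 8.5, 11.5 and 11.7 add telephone, email, contact with the treating team, general-practitioner confirmation and routine clinic review. A missed questionnaire is not automatically a missing outcome. This lowers the likely amount of loss but does not remove the 12% that the plan assumes.
- **The fragile cases are chosen.** The 16% and 5.9% rates, the loss rates and the odds ratios are assumptions. At the protocol's own effects both trials withstand an odds ratio of 5. This stands, and it limits the severity.
- **MAST-PROPHYLAXIS is different.** Its outcome is at two weeks, with inpatient observation and a day-14 contact. It should not be treated as equally exposed.

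**Conclusion.** The point holds in a limited form. The sensitivity analysis that 16.5 names cannot show whether outcome-related loss changes the answer, so it cannot on its own deliver the assessment of missing data promised in 16.1. The practical weight falls on MAST-DURATION with a moderate observed effect. There, 7 seizures among 26 lost long-course patients instead of about 4 would remove significance, and no analysis named in the protocol would reveal it. At the full design effect, about 14 to 15 of 26 would be needed, so the planned result is robust to all but large departures from MAR.

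These sizes rest on 12% loss split equally between arms, lost control patients having seizures at the control rate, unadjusted two-proportion tests, and the assumed rates marked above. The figures do not show that the primary analysis will be biased, or that the sample size is wrong. This is a change that should be made, not a flaw that invalidates the design.

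**What to change.** In section 16.5, add a pre-specified delta-adjusted (tipping-point) analysis of the primary outcome. Impute missing outcomes under MAR, shift the seizure risk of missing patients separately by arm over a stated range, and report the risk difference with its confidence interval across that range and the point at which significance is lost. Make MAST-DURATION the priority. For MAST-PROPHYLAXIS, apply it to each comparison with control using that trial's own Dunnett-based threshold. Keep complete case as supplementary.

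The cost is a sentence or two of protocol text and a few hours of programming, with no change to sample size, visits or data collection. It should be fixed before unblinded data are seen. The small downside is that a borderline result may be shown to be fragile.
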